Subject will receive up to 3 doses of CYNK-001 on Days 1, 4, and 7. A minimum of 2 doses is required for efficacy assessment. After the first dose, subsequent infusions on Days 4 and 7 will be provided only if no toxicity of Grade 3 and above (either related or unrelated to CYNK-001) is observed.

Study Design:

The study will include a Phase I portion wherein a total of 14 subjects will be enrolled to assess the safety and efficacy of CYNK-001. To evaluate the safety for potential dose limiting toxicities (DLTs), this phase will enroll 3 subjects initially treated with CYNK-001. The safety data for these 3 subjects will be evaluated 24 hours after the final dose was provided to the 3rd subject.

If deemed safe, the remaining 11 subjects will be enrolled and monitored per the safety stopping rule until Study Day 15 where the first CYNK-001 infusion occurs on Day 1. If any DLT is observed in the first three subjects, the DMC will be convened for a recommendation. For the remaining 11 subjects, DMC will be convened if the safety stopping rule is met. Overall, in case of 2 out of the 6 subjects had experienced DLTs in the Phase I portion of this study, the DMC will be convened for safety evaluation. Subjects treated in the Phase I portion of the study will be treated in the inpatient setting.

The starting dose of 150×10^6 cells was selected as a desensitizing dose on Day 1 followed by 600×10^6 cells on Days 4 and 7. The DLTs will be evaluated through Study Day 28 following the first dose of CYNK-001 infusion (Day 1). Once CYNK-001 is deemed safe per the stopping rules and if efficacy is established in at least 2 out of the 14 subjects by Study Day 15, Phase II portion of the study will be initiated.

The Phase II portion of the study is a randomized, open-label, multi-site study. Subjects will be randomized into either CYNK-001 or Control group with best supportive care alone as defined by the institutional practice by 1:1 ratio. All subjects in both Phase I and Phase II will receive the best supportive care. Subjects treated in the Phase II portion of the study may be treated in the outpatient setting, if deemed safe based on Phase I data review and recommendation by the DMC.

The study is divided into 3 study periods:

Screening Period

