This study will enroll up to 86 subjects in total, with 14 subjects in the Phase I portion and up to 72 subjects with a 1:1 randomization ratio to either CYNK-001 or the best supportive care control arm as defined by the institutional practice in the Phase II portion of the study.

Investigational product, dosage and mode of administration:

CYNK-001 dosage and mode of administration:

Dose Level 1: CYNK-001 with an initial Dose of 150×10^6 cells on Day 1 followed by 600×10^6 cells on Days 4 and 7 (second and third doses). After the first dose, subsequent infusions on Days 4 and 7 will be provided only if no toxicity of Grade 3 and above (either related or unrelated to CYNK-001) is observed for each subject. If any such \geq Grade 3 toxicity is observed, the second and third doses will be delayed up to 48 hours until the noted event is resolved or reduced to Grade 1 toxicity level.

Dose de-escalation Level -1: Dose de-escalation is defined as reducing the frequency of the doses (without reducing the total number of cells given per dose) by providing doses only on Days 1 and 7 for any potential safety concerns per DMC recommendation. CYNK-001 with an initial dose of 150×10^6 cells on Day 1 followed by 600×10^6 cells on Day 7.

CYNK-001 is to be administered IV using a gravity IV administration set with a 16- to 22- gauge (or equivalent) needle or catheter with no filters. A central line may be used to infuse CYNK-001 after confirming that the catheter diameter is 16- to 22- gauge (or equivalent) needle. For substantial deviation from this catheter diameter consultation with the medical monitor is required. The recommended infusion rate is approximately 240 mL per hour.

Subjects will receive pre- and post- medication of acetaminophen (650mg PO) and diphenhydramine (25mg PO/IV) at least 30 minutes prior to and approximately 4 hours after each CYNK-001 infusion.

Vital signs will be taken prior to, approximately 30 minutes after the start, and approximately 4 hours after the completion of each infusion. Subjects must be monitored for at least 4 hours after completion of each CYNK-001 infusion.

Dose Modifications

Dose adjustments may occur if clinically indicated by the treating physician. In general, the following should be followed:

- Dose reductions are not permitted in this study. If DLTs safety concerns are observed, the dose de-escalation treatment with reducing frequency of doses will be implemented per DMC recommendation.

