6.3. Dose Limiting Toxicity (DLT) Definition

Known pathologies associated with COVID-19 will be carefully considered and differentiated from potential CYNK-001-related effects in order to identify CYNK-001 related toxicities. Adverse events occurring up to Day 28 from the first dose of the CYNK-001 infusion will be included in the dose-limiting toxicity (DLT) determination.

A DLT is defined as the development of any new (not pre-existing) events:

- Grade 4 or 5 event in any organ system
- Grade 4 > 24 hour (Due to known organ damage associated with the COVID-19) in the following organ systems:
 - Cardiac
 - Pulmonary
 - Hepatic
 - Renal
 - Central Nervous System (CNS)
- Grade 3 or above allergic reaction that is suspected to be related to CYNK-001.
- Grade 3 or above GvHD event occurring within the first 28 days following CYNK-001 infusion (to Study Day 28).
- Grade 3 or above CRS event occurring within the first 28 days following the first CYNK-001 infusion (to Study Day 28).

All above events to be identified in discussion with the clinical study Medical Monitor and reportable to Drug Safety.

The events will be assessed for the first 3 subjects in Phase I and per the study stopping rules for the remaining subjects. Any such findings will be forwarded to the DMC for recommendation, review and confirmation as to whether or not the maximal tolerated dose (MTD) has been exceeded. If the MTD is confirmed by the DMC, no further CYNK-001 administration will occur within that dose level or at any higher dose level. For the remaining 11 subjects, DMC will be convened if the safety stopping rule is met. Overall, in case of 2 out of the 6 subjects had

experienced DLTs in the Phase I portion of this study, the DMC will be convened for safety evaluation.

During Phase II portion of the study, DMC will be convened at midpoint (after 18 subjects have received treatment) to evaluate safety for adverse event of interest such as shock, ARDS, and death in the treatment group versus the control group.

MTD is defined as the highest CYNK-001 dose level wherein it was deemed safe per the defined stopping rules or if the DMC recommends stopping the study due to DLTs suspected to be related to CYNK-001.

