6.4. Treatment Assignment

Phase I:

Upon confirmation of eligibility during the Screening Period, eligible subjects will be sequentially assigned to the CYNK-001 group at the time of eligibility based on treatment slot availability.

Dose Level cohorts:

- Dose Level 1: CYNK-001 with an initial IV dose of 150×10^6 cells on Day 1 followed by 600×10^6 cells CYNK-001 IV on Days 4 and 7. After the first dose, subsequent infusions on Days 4 and 7 will be provided only if no toxicity of \geq Grade 3 (either related or unrelated to CYNK-001) is observed for each subject. If any such \geq Grade 3 toxicity is observed, the second and third doses will be delayed up to 48 hours until the noted event is resolved or reduced to Grade 1 toxicity level.
- Dose de-escalation Level -1: CYNK-001 with an initial IV dose of 150×10^6 cells on Day 1 followed by 600×10^6 cells CYNK-001 IV on Day 7 will be implemented due to potential safety concerns per the DMC recommendation.

A total of 14 subjects will be treated in the Phase I portion of the study.

Phase II:

For the Phase II portion of the study, up to 72 subjects will be randomized into the study with 1:1 ratio to either CYNK-001 or the control arm (best supportive care). The Phase II portion of the study is a randomized, open-label, multi-site study. Subjects will be randomized into either CYNK-001 group or Control group with 1:1 ratio stratified by age (< 45 vs. ≥ 45 years old).

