9.1.2. CYNK-001 Overdose

On a per dose basis, an overdose is defined as the following amount over the protocol-specified dose of CYNK-001 assigned to a given subject, regardless of any associated AEs or sequelae:

CYNK-001: 30% over the assigned protocol-specified dose of 600×10^6 cells.

On a schedule or frequency basis, an overdose is defined as anything more frequent than the protocol required schedule or frequency.

Complete data about drug administration, including any overdose, regardless of whether the overdose was accidental or intentional, should be reported in the eCRF. (Refer to [Section 12.3.1.1](#) for overdose reporting requirements).

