12.3. Adverse and Serious Adverse Events

12.3.1. Definition of Adverse Events

12.3.1.1. Adverse Event (AE)

An AE is the development of an undesirable medical condition or the deterioration of a pre-existing medical condition following or during exposure to a pharmaceutical product, whether or not considered causally related to the product. In clinical studies, an AE can include an undesirable medical condition occurring at any time, including baseline or washout periods, even if no study treatment has been administered.

An AE is any noxious, unintended, or untoward medical occurrence that may appear or worsen in a subject during the course of a study. It may be a new intercurrent illness, a worsening concomitant illness, an injury, or any concomitant impairment of the subject's health, including laboratory test values, regardless of etiology. Any worsening (i.e., any clinically significant adverse change in the frequency or intensity of a pre-existing condition) should be considered an AE. A diagnosis or syndrome should be recorded on the AE page of the eCRF rather than the individual signs or symptoms of the diagnosis or syndrome.

Abuse, withdrawal, sensitivity or toxicity to an investigational product should be reported as an AE. Overdose, accidental or intentional, whether or not it is associated with an AE should be reported on the overdose eCRF. (See [Section 9.1.2](#) for the definition of overdose.) Any sequela of an accidental or intentional overdose of an investigational product should be reported as an AE on the AE eCRF. If the sequela of an overdose is an SAE, then the sequela must be reported on an SAE report form and on the AE eCRF. The overdose resulting in the SAE should be identified as the cause of the event on the SAE report form and eCRF but should not be reported as an SAE itself.

In the event of overdose, the subject should be monitored as appropriate and should receive supportive measures as necessary. There is no known specific antidote for CYNK-001 overdose. Actual treatment should depend on the severity of the clinical situation and the judgment and experience of the treating physician.

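### Two safety definitions do not work as literally written: the only overdose limit does not fit the Day 1 dose, and the first DLT item cancels the 24-hour allowance in the second

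*Protocol*

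**What the plan says.** **Overdose.** Protocol 9.1.2 opens with a general rule: "On a per dose basis, an overdose is defined as the following amount over the protocol-specified dose of CYNK-001 assigned to a given subject". The amount that follows is "30% over the assigned protocol-specified dose of" 600×10^6 cells, and no other quantity is given. A second rule in the same section covers only dosing that is too frequent. Under Protocol 6.4 the regimen is "Dose Level 1: CYNK-001 with an initial IV dose of" 150×10^6 cells on Day 1, then 600×10^6 on Days 4 and 7. The synopsis says that the 150×10^6 dose "was selected as a desensitizing dose on Day 1 followed by" the larger doses. Protocol 12.3.1.1 attaches a reporting duty: "Overdose, accidental or intentional, whether or not it is associated with an AE should be reported on the overdose eCRF".

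**DLT.** Protocol 6.3 and the synopsis list the new events that count as DLTs. The first item is "Grade 4 or 5 event in any organ system". The second is a Grade 4 event lasting more than 24 hours in the cardiac, pulmonary, hepatic, renal or central nervous systems, with known COVID-19 organ damage given as the reason. Further items cover allergic reaction, GvHD and CRS at Grade 3 or above.

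**DMC trigger.** The synopsis and Protocol 6.1, 6.3 and 14.10 say that the DMC is convened if two of six Phase I subjects have DLTs. The Phase I groups named are the first 3, the remaining 11 and all 14. SAP 3 describes the Phase I design without this trigger.

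**The concern.** Both definitions are stated rules that sites would follow, and followed literally each gives a result that the sponsor probably did not want.

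For overdose, giving the Day 4 quantity on Day 1 is a foreseeable error in a step-up regimen, and it defeats the purpose of a desensitizing dose. The stated figure leaves it unlabelled. What hangs on the label is the overdose eCRF, the monitoring and supportive measures in Protocol 12.3.1.1, and the naming of the overdose as the cause on the SAE form if a serious sequela follows.

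For DLTs, the second item gives a reason for leniency in five organ systems, but nothing makes it an exception to the first. Two sites could classify the same 12-hour Grade 4 pulmonary event differently. DLT status matters for convening the DMC in the first 3 subjects (Protocol 14.10) and for notice to the DMC Chair (14.11.2).

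For the two-of-six trigger, the rule for subjects 4 to 14 that otherwise convenes the DMC is death. Two-of-six is therefore the only automatic meeting rule based on non-fatal DLTs after subject 3, and the six are not identified.

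**Working it through.** The plan states no calculated figure on these points, so there is none to reproduce.

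**1. Overdose limit** (inputs: 30% and 600×10^6 from Protocol 9.1.2; 150×10^6 from 6.4)
- Limit as written: 1.3 × 600×10^6 = 780×10^6 cells.
- Relative to the Day 1 dose: 780/150 = 5.2, so a Day 1 infusion up to 420% over plan is not flagged.
- Full later dose given on Day 1: 600/150 = 4 times plan, and 600 < 780, so not an overdose by the stated figure.
- Same 30% applied to Day 1: 1.3 × 150×10^6 = 195×10^6 cells.
- The frequency rule does not catch this error, because the number and timing of infusions are unchanged.

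**2. DLT items** (inputs: the first two items in Protocol 6.3)

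| Event | Item 1 | Item 2 | DLT as written | DLT if item 1 is narrowed |
|---|---|---|---|---|
| Grade 5, any system | yes | no | yes | yes |
| Grade 4, other system, any duration | yes | no | yes | yes |
| Grade 4, five systems, over 24 h | yes | yes | yes | yes |
| Grade 4, five systems, 24 h or less | yes | no | yes | no |

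No row is a DLT through item 2 alone. The last row is the only one that changes under the narrowed wording, and such an event would still count if it met the allergic, GvHD or CRS item.

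**3. Two-of-six trigger.** No document gives a DLT rate, so assume p = 10%, 20% or 30% per subject, independent, with q = 1 − p. Keep the rule that any DLT in the first 3 convenes the DMC. The chance of a mandatory DLT-based meeting is then:
- Six read as the first six treated: 1 − q³(q³ + 3pq²)
- Two or more among all 14: 1 − q³(q¹¹ + 11pq¹⁰)

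| p | First six | All 14 | Difference |
|---|---|---|---|
| 10% | 1 − 0.729(0.729 + 0.243) = 0.29 | 1 − 0.729(0.3138 + 0.3835) = 0.49 | 0.20 |
| 20% | 1 − 0.512(0.512 + 0.384) = 0.54 | 1 − 0.512(0.0859 + 0.2362) = 0.84 | 0.29 |
| 30% | 1 − 0.343(0.343 + 0.441) = 0.73 | 1 − 0.343(0.0198 + 0.0932) = 0.96 | 0.23 |

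Differences are taken before rounding. Each is the chance of at least two DLTs among 14 with no DLT-based meeting trigger met. If the six are any six consecutive subjects, enumeration of all DLT patterns gives 4.2%, 4.1% and 1.9%. If any six subjects qualify, consecutive or not, it is 0. For the 7 subjects dosed, the first-six reading gives q³ × 3pq² × p = 1.8%, 3.9% and 4.5%. All are upper bounds on having no extra meeting, since deaths and Chair requests can also convene the DMC.

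**The case against.** **The overdose intent is recoverable.** The lead-in speaks of each dose and of the dose assigned to the subject, so a sensible reader would apply 30% to 150×10^6 on Day 1. That stands, and it limits the weight of the point. It does not remove it, because the operative line names one quantity. Section 9.1.1, Tables 4 and 5 and most of Section 10 are not in the available text. What remains of Section 10 gives instructions specific to the second and third doses, so a per-infusion limit may exist there.

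**A reader might infer that a Day 1 error would go unrecorded or unwatched.** The documents do not support that. Section 9.1.2 itself requires "Complete data about drug administration, including any overdose", the synopsis says "Subjects must be monitored for at least 4 hours after completion of each CYNK-001 infusion", and protocol deviations are summarized (Protocol 14.4).

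**A reader might infer that DLTs would be missed.** The overlap works the other way: it counts more events. Protocol 6.3 also opens by saying that COVID-19 pathology will be distinguished from product effects, has events identified with the Medical Monitor, and 6.5 leaves de-escalation to the DMC's recommendation. Treating the second item as qualifying the first is a natural reading, but the text does not say so.

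**A reader might infer that the six are defined nowhere, or that the DMC would not see later DLTs.** Neither follows. Protocol 14.11.2 and SAP 8 refer to a DMC charter that was not available and may name the six. Every DLT is forwarded to the DMC (Protocol 6.3, SAP 3), its Chair is told within 24 hours, any death by Day 15 stops the study, and the DMC meets after subject 3 and again after Day 15 of the last Phase I subject. Only the timing of a mandatory meeting is open.

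**Conclusion.** The point holds for the two definitions, at minor severity. The single overdose limit is 5.2 times the Day 1 dose and, taken literally, does not cover a fourfold error on the desensitizing infusion. The second DLT item has no effect beside the first, so the 24-hour allowance does not operate. Both conclusions follow from the text and need no assumed rate. The overdose conclusion is subject to the unavailable Section 9.1.1 and Tables 4 and 5.

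The two-of-six trigger is a secondary point: it matches no group named in the protocol or SAP. How much the reading matters depends on assumed DLT rates and on a charter that may settle it.

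None of this affects an efficacy endpoint, the sample size or the rule for moving to Phase II. SAP 15 records closure after 7 Phase I subjects. Its reduced analysis list keeps adverse event summaries but names no DLT table. What remains at stake is consistent classification in the brief report and any reuse of this protocol text.

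**What to change.** - **Protocol 9.1.2:** define overdose as 30% over the protocol-specified dose for that infusion (above 195×10^6 cells on Day 1; above 780×10^6 cells on each later infusion). This also fits the de-escalated schedule of Days 1 and 7.
- **Protocol 6.3 and synopsis:** if the allowance is intended, change the first DLT item to a Grade 5 event in any organ system, or a Grade 4 event outside the five organ systems listed below, and keep the second item. If no allowance is intended, delete the second item.
- **Synopsis, Protocol 6.1, 6.3 and 14.10:** the sponsor and DMC should name the six subjects meant, consistent with the charter.

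The first two changes are wording only and add no procedures. Naming the six is also wording only if it records what was already intended. Replacing the trigger with two or more of all treated Phase I subjects is a different matter. Against the first-six reading, it would raise the chance of a mandatory DLT-based meeting from 0.29/0.54/0.73 to 0.49/0.84/0.96 at assumed DLT rates of 10/20/30%. That is an option with a cost in DMC meetings, for the sponsor and DMC to choose or decline.

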9.2. Concomitant Medications

Over the course of this study, additional medications may be required to manage aspects of the disease state of the subjects, including side effects from trial treatments or clinical worsening. Supportive care, including but not limited to antiemetic medications, may be administered at the discretion of the physician. Use of high-dose steroids (greater than or equal to 0.5mg/kg per day prednisone equivalent) is not recommended during the Treatment Period, unless clinically indicated and at the discretion of the treating physician. High-dose steroids have been shown to interfere with the effectiveness of some adoptive cell therapies. If clinically indicated, careful consideration should be taken regarding the timing and tapering of high-dose steroids.

All concomitant treatments, including blood and blood products, used from 28 days prior to the first CYNK-001 infusion until completion of the study must be reported on the eCRF. All treatments administered for the purposes of providing care of COVID-19 including name and number of doses must be reported on the eCRF.

For information regarding other drugs that may interact with CYNK-001 and affect CYNK-001 activity, please see the IB.

9.2.1. Permitted Concomitant Medications

All subjects are to receive standard medical care for COVID-19 signs and symptoms, unless contraindicated.

During the Treatment Period and Follow-Up Period, the following Concomitant Medications are permitted:

- Prophylactic antibiotic and antifungal medication are permitted at the discretion of the treating physician. These treatments must be identified as prophylactic in the physical examination source documents.
- Diphenhydramine and acetaminophen are permitted to be used as indicated before and after CYNK-001 administration and as clinically indicated.
- Meperidine is permitted for the control of rigors and as clinically indicated.
- Steroids are permitted if clinically indicated and at the treating physician's discretion during the treatment period. If clinically indicated, careful consideration should be taken regarding the timing and tapering of high-dose steroids.
- Blood product transfusions may occur as clinically indicated greater than 24 hours before or greater than 24 hours after CYNK-001 infusion.
- Supplemental oxygen therapy is permitted if clinically indicated.
 - Note: Per NIH COVID-19 Treatment Guidelines dated 17 December 2020, the optimal target SpO₂ in adults with COVID-19 is between 92% and 96%. (<https://www.covid19treatmentguidelines.nih.gov/critical-care/oxygenation-and-ventilation/>; [NIH COVID-19 Treatment Guidelines: Oxygenation and Ventilation, 17 December 2020](#))
- Concomitant therapy with potential activity against COVID-19 is permitted.

9.2.2. Prohibited Concomitant Medications

- Blood product transfusions should not occur within 24 hours prior to and/or 24 hours after CYNK-001 infusion, unless clinically indicated.

9.2.3. Required Concomitant Medications

- The best supportive care treatments must be identified in the source documents and documented that they are administered for COVID-19. Prophylactic use of any treatment during the study must be documented as prophylactic treatment.
- Subjects should receive adequate medical therapy for control of hypertension, diabetes, and any other chronic medical conditions for which they require ongoing care.

[figure not shown]
[figure not shown]
- Acetaminophen and diphenhydramine are required concomitant medications to be administered prior to and following each CYNK-001 infusion.
- In some cases, tocilizumab, an anti-IL-6R-antibody, may be required to treat toxicities such as Cytokine Release Syndrome (CRS). Please refer to currently approved Actemra® package insert ([Actemra, 2019](#)). The recommended dose to intervene in subjects with CRS is 8 mg/kg; however, dosing is at the discretion of the treating physician. Other similarly available immune-modulatory drugs (targeted biologics), but not corticosteroids or more broadly-acting immunosuppressants) could be considered per physician discretion.

[figure not shown]

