9.3. Treatment Compliance

[figure not shown]
CYNK-001 is to be administered IV at the clinical study site. Study personnel will review the dosing treatment allocation and ensure treatment is administered according to the subject's treatment plan. Treatment compliance will be noted on the appropriate CRFs and source records based on administration records.

- Dose reductions are not permitted in this study.
- Dose delays are permitted. See [Section 6.5](#)
- Concomitant therapies
 - Blood product transfusions should not occur within 24 hours prior to and/or 24 hours after CYNK-001 infusion.
 - Use of steroids is permissible if clinically indicated and at the discretion of the treating physician.

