12.6.2.3. Cytokine Release Syndrome Management

During the ASTCT consensus on the CRS grading, a need for variation in practitioner intervention for CRS treatment was recognized. The below Algorithm provides one of the key recommendations for CRS treatment while allowing investigators to maintain their usual practice.

Figure 3: Cytokine Release Syndrome Treatment Algorithm

Adapted/modified from [Lee, 2014](#)

All subjects at time of CYNK-001 treatment:
 
 • Monitor for CRS symptoms (fever, fatigue, anorexia, neurologic changes) • Follow serum CRP, ferritin, and coagulation as clinically indicated

Grade 1 CRS
 
 • Evaluate fever, take surveillance cultures, give antibiotics per institutional guidelines • Admit and monitor closely for organ dysfunction, include neurologic exams if clinically indicated • Follow CRP, ferritin, and coagulation daily • Symptomatic support (e.g., antipyretics) • If rapid progression from time of first fever, and/or CRP rising quickly within 96 hours, recommend Tocilizumab

Grade 2 CRS
 
 • Frequent inpatient monitoring until fever and symptom resolution, include neurologic evaluations if clinically indicated • Follow CRP, ferritin, and coagulation daily • Symptomatic, hemodynamic, and respiratory support • Initiate seizure prophylaxis if clinically indicated, consider EEG monitoring • Recommend Tocilizumab • If CRS rapidly progressing (progressive hypotension, neurologic symptoms, and/or rapid rise in CRP) or refractory to tocilizumab, recommend corticosteroids

Grade 3 CRS
 
 • ICU-level monitoring until stable, include neurologic exams if clinically indicated • Follow CRP, ferritin, and coagulation daily • Symptomatic, hemodynamic, and respiratory support • Initiate seizure prophylaxis if clinically indicated, consider EEG monitoring • Recommend Tocilizumab • Recommend corticosteroids every 12 to 24 hours • If CRS rapidly progressing recommend increased dose and frequency of corticosteroids and/or other IL-6 blocking agents

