
Grade 4 CRS
 
 • ICU-level monitoring until stable, include neurologic exams if clinically indicated • Follow CRP, ferritin, and coagulation daily • Symptomatic, hemodynamic, and respiratory support • Initiate seizure prophylaxis if clinically indicated, consider EEG monitoring • Recommend Tocilizumab • Recommend corticosteroids every 6 to 12 hours • If CRS persists, recommend increased dose and frequency of corticosteroids and/or other IL-6 blocking agents

Abbreviations: CRP = C-reactive protein; CRS = cytokine release syndrome; EEG = electroencephalogram; IL = interleukin; ICU = intensive care unit

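### Read literally, Protocol 9.2.3 excludes corticosteroids for CRS; Figure 3 recommends them at Grades 2 (conditionally), 3 and 4, and no text says which governs

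*Protocol*

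**What the plan says.** Protocol 9.2.3, under required concomitant medications, says tocilizumab may be needed for toxicities such as CRS. It then adds that other similar drugs, described as targeted biologics, "but not corticosteroids or more broadly-acting immunosuppressants) could be considered per physician discretion".

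The CRS algorithm in Protocol 12.6.2.3 (Figure 3) treats the same toxicity grade by grade. At Grade 2 it recommends corticosteroids if the event progresses rapidly or does not respond to tocilizumab. At Grade 3 it lists tocilizumab and, as a separate item, "Recommend corticosteroids every 12 to 24 hours". At Grade 4 it again lists tocilizumab and "Recommend corticosteroids every 6 to 12 hours".

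Three other sections deal with steroids in general, without mentioning CRS. Section 9.2 advises against high-dose steroids in the Treatment Period unless clinically indicated, and gives the reason: "High-dose steroids have been shown to interfere with the effectiveness of some adoptive cell therapies". Sections 9.2.1 and 9.3 permit steroids when clinically indicated. In 12.6.2.2, a footnote to the CRS grading table allows for patients with CRS who then receive tocilizumab or steroids.

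Peri-infusion transfusion is also covered in three places. Section 9.2.1 permits transfusion more than 24 hours before or after an infusion. Section 9.2.2 discourages it inside those windows but ends with an exception: "CYNK-001 infusion, unless clinically indicated". The compliance rule in 9.3 has no exception: "Blood product transfusions should not occur within 24 hours prior to and/or 24 hours after CYNK-001 infusion".

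**The concern.** An investigator managing a Grade 3 event who opens 9.2.3 finds corticosteroids excluded from the further options. One who opens Figure 3 finds them recommended. Nothing in either place points to the other.

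This matters more than most wording slips for three reasons.

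- **The toxicity is a safety trigger.** CRS of Grade 3 or above within 28 days of the first infusion is a dose-limiting toxicity (Protocol 6.3). A DLT goes to the DMC Chair within 24 hours of the sponsor being informed (14.11.2), and new or worsening CRS of any grade is immediately reportable (12.1).
- **It is foreseeable.** Section 12.6.2 says that PNK-007, described as comparable to CYNK-001, has been associated with CRS, and 12.3.1.6 says the Investigator's Brochure lists CRS as expected.
- **The choice may bear on efficacy as well as safety.** The protocol itself warns that high-dose steroids can weaken some cell therapies. If sites differ in giving them, later OSCI and NEWS2 readings in affected subjects may partly reflect which section was consulted. The SAP's per-protocol population (Section 7) excludes subjects with major deviations that may affect the primary outcome, so whether steroids given under Figure 3 departed from 9.2.3 could be disputed.

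**Working it through.** No arithmetic applies: neither passage contains a figure to reproduce. The check is to set the passages side by side, confirm that they cover the same situation, and look for text that reconciles them.

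**Step 1. Same situation?** Yes. The 9.2.3 bullet is about treating toxicities such as CRS, and Figure 3 is the CRS algorithm for subjects treated with CYNK-001.

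**Step 2. Same instruction?**

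| CRS grade | Figure 3 on corticosteroids | 9.2.3 read literally | Agree? |
|---|---|---|---|
| 1 | Not mentioned | Excluded from the other drugs to consider | Yes |
| 2 | Recommended if progressing rapidly or not responding to tocilizumab | Excluded | No, under that condition |
| 3 | Recommended, listed with tocilizumab | Excluded | No |
| 4 | Recommended, listed with tocilizumab, at shorter intervals | Excluded | No |

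Three of the four grades conflict, one of them conditionally. At Grades 3 and 4 the recommendation does not depend on tocilizumab having failed. The two texts do agree on targeted agents: Figure 3 allows other IL-6 blockers at Grades 3 and 4, and 9.2.3 allows other targeted biologics. The disagreement is confined to corticosteroids.

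**Step 3. Does any other text reconcile them?** Sections 9.2, 9.2.1 and 9.3 show that steroids are not barred from the study, and the grading footnote shows that the authors expected some use in CRS. None of these refers to the 9.2.3 exclusion, says that it is limited to certain circumstances, or says which section takes precedence.

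**Step 4. Transfusion.** Take one case: a clinically indicated transfusion 12 hours after an infusion.

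- 9.2.1: outside what is listed as permitted, since 12 hours is less than 24.
- 9.2.2: allowed, through its exception.
- 9.3: contrary to the compliance wording, which has no exception.

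The same act therefore gets different answers from different sections.

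**Step 5. How many subjects?** This cannot be derived. The documents give no CRS rate by grade, and SAP Section 15 reports that the trial closed with 7 subjects enrolled and dosed in Phase I.

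**The case against.** The best defence is that 9.2.3 only defines acceptable substitutes for tocilizumab. The sentence speaks of similar drugs, and its brackets are unbalanced, which suggests that the words about corticosteroids were meant to sit inside a parenthesis describing that class. Figure 3 does not offer steroids as a substitute: it adds them to tocilizumab or uses them after it. On this reading both texts can be followed. The heading of 9.2.2, which lists what is prohibited, names only transfusion, and every general statement on steroids permits them when indicated. One ambiguous clause would then stand against the rest of the protocol.

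This reading is plausible, and it rules out saying that the protocol bans steroids. It does not settle the matter: no sentence states it, and a site should not have to infer a rescue rule from a misplaced bracket.

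A second objection also has force. The text introducing Figure 3 presents it as a recommendation and leaves investigators their usual practice, so some variation between sites is accepted by design. It follows that sites may differ because of this conflict, not that they will. Making Figure 3 advisory does not remove the exclusion in 9.2.3.

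Third, a CRS event is a DLT once it reaches Grade 3, and steroid choice afterwards cannot undo that classification. This is correct. What remains at stake is the management of the event and the Grade 2 decision, which comes before the threshold.

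On transfusion, 9.3 does not actually say that a transfusion allowed by 9.2.2 is to be recorded as non-compliance, so that point is minor.

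**Conclusion.** The point holds as an unresolved conflict in the current protocol. On a literal reading, 9.2.3 excludes what Figure 3 recommends for conditional Grade 2 and for Grade 3 and Grade 4 CRS, and nothing says which text governs. It deserves correction because it concerns rescue from a DLT-level toxicity. The conclusion depends on the wording alone, not on any assumed event rate.

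Three stronger conclusions that a reader might draw are not supported.

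- **That CRS rescue happens only in the CYNK-001 arm, so the conflict biases the comparison.** Protocol 6.1 includes IL-6 and GM-CSF inhibitors aimed at CRS morbidity in best supportive care, which all subjects receive. Only CRS attributed to CYNK-001 is specific to that arm.
- **That sites will treat the same event differently.** This is possible, not shown.
- **That a number of affected subjects can be stated.** Any count would need an invented CRS rate. Applying it to the planned 50 CYNK-001 subjects (14 in Phase I plus 36 in Phase II) would also use a base that was not reached. With 7 subjects dosed, all in the single-arm Phase I, no between-arm effect can have arisen.

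The transfusion mismatch is real but secondary.

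**What to change.** 1. **Main change.** The sponsor's medical team should reconcile 9.2.3 with Figure 3 and with 9.2, 9.2.1 and 9.3, so that they give one instruction on corticosteroids for CRS, and add cross-references. The revised text should also say how the caution in 9.2 applies once CRS is being treated. The clinical content is theirs to decide.
2. **Secondary change.** Bring the peri-infusion transfusion wording in 9.2.1, 9.2.2 and 9.3 into agreement, so that any exception appears in the compliance rule as well or in neither place.
3. **Optional.** Protocol 12.1.7 already collects the reason for each medication and SAP 16.1 already lists it, but the SAP's frequency summaries are by treatment group only. Coding whether each steroid or IL-6 blocker course was given for COVID-19 or for CRS would allow a tabulation by arm in a two-arm study. For the 7 Phase I subjects, a listing with the reason for use would be enough.

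The first two cost a wording amendment. The third costs one coded value on an existing form and one table. Since the trial has closed, the wording changes matter mainly if this protocol is reopened or reused as a template.
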